5.1. Selection of the study Population

The study population will consist of at least 200 participants who have completed the self-enrollment form and who meet the inclusion-exclusion criterion. The participants will otherwise be in good health.

The target sample size for this study is initially 200 participants, with a desired sample of 80 treated participants This sample size has been calculated to provide a reasonable estimate of the time to cold resolution, as further described in detail in the Statistical Considerations section.

At such time as 180 participants have been enrolled, the available data will be analyzed using a constant hazard model to determine if it seems realistic that the desired number of 80 treated participants will be met by the end of follow-up. If the expected number of treated participants is less than 80, the target sample size will be increased as needed, considering both the desire for 80 treated participants and the timelines of the trial sponsor. The actual outcomes of treated participants will not be considered in this analysis, merely whether or not enrolled participants have reported starting using the test product.

Enrollment will be stopped once the target number of participants have been enrolled; no further participants will be offered a place in the trial once the target sample size criteria has been met. All participants who have already been offered places, but who have not yet consented, will be allowed to participate as long as they have signed the study consent within 15 days and the total number of participants does not exceed 125% of the target (either 200 or the recomputed target if recomputation has been performed).

In order to ensure an age and sex distribution that is reasonably representative of the US population, enrollment may be stopped early in some age and sex groups.

Target population for this study are candidates who are in the general population who are seeking herbal remedies to reduce the duration of their common cold symptoms.

Participants will be enrolled from across the United States. No participants will be enrolled outside of the United States. It is expected that the geographical distribution of the participants enrolled in the study will correlate with the geographical distribution of the general population across the United States.

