7.2. Sample Size Considerations

The referenced paper of Mossad, Macknin, et al. had a sample size of 100 patients with colds, of which 50 were in the treatment arm. Based on informal readings of various sources, we estimate that approximately 40% of the enrolled participants in this trial will experience a cold during the 90-day period. A sample size of 200 enrolled participants would then yield 80 participants with colds. Even with the uncertainties of compliance in this trial, the sample size should enable reasonable comparison of results against the Mossad, Mackin et al. study. [20]

As discussed above, the number 200 may be increased based on observed data concerning the number of participants with colds. The actual outcomes of treated participants will not be considered in this analysis, merely whether or not enrolled participants have reported starting using the test product. The method of reevaluating the sample size will be described in the Statistical Analysis Plan.

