7.3. Analysis Plan

Time-dependent variable analysis

The primary analysis involves time dependent variables. The Kaplan-Meier algorithm will be used to analyze time to freedom from cold symptoms. Data presentation will include tables and graphs; in particular tables of participants at risk at various time points.

Censoring:

- Participants who do not have a cold during the trial will not be in the ITT population, and will
 not be included in the endpoint analysis.
- Participants who report the onset of a cold, but who do not complete the daily reports through
 18 days will be censored as of the date of the last report.
- Participants who still have cold symptoms at 18 days will be censored at that time.
- Participants will also be censored if they withdraw from the trial.

Secondary Endpoints:

- Analysis of the individual cold symptoms will be a presentation of median time until the
 individual symptom resolves. The median for this purpose is the value computed as part of
 the Kaplan-Meier algorithm.
- An additional analysis will investigate the relation between baseline age and gender, and the time to resolution.
- Adverse events will be summarized.
- An additional data presentation will consist of side by side presentation of results from both

Treatment and Control in similar studies appearing in the literature. There will be no formal statistical comparison of results from this study and historical studies.

General statistical methods:

Data will be analyzed using standard statistical methods, as further specified in a statistical analysis plan (SAP), which will be prepared in detail at a later date. [23]

- Data analysis will largely consist of summary statistics and graphs. The only formal statistical comparisons will be in covariate analyses.
- For continuous variables data presentation will consist of means, confidence intervals computed using the *t*-statistic, medians, and interquartile ranges. Group comparisons will use *t*-tests or ANOVA.
- For discrete variables confidence intervals will use the exact intervals, where available. Group comparisons will use Fisher's exact test, with the Monte Carlo version used where computationally necessary.
- For time to event variables analysis will use the Kaplan-Meier algorithm, and group comparisons will use the log-rank or proportional hazards methods, depending on the data type.
- Covariate analyses will investigate the relation between baseline and outcome variables, using

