 methods appropriate to the data types involved. Age, gender, and baseline medications will be
 included in these analyses where appropriate data are available.
- Present intention is that the analysis will be performed in R, and the precise form of algorithms will be the default of R. Kaplan-Meier, log-rank, and proportional hazards algorithms will be the defaults of the survival package.
- Visual analog scale values will be treated as continuous variables. Frequency counts will also be provided for scales with 10 or fewer distinct response levels.
- The exact items to be compared depend on what is reported in each historical control study. When possible, the items will include time to resolution of all cold symptoms, time to resolution of each individual cold symptom, proportion of cold symptoms resolved at each time, and reported baseline characteristics. When two-arm studies are compared, both arms will be reported in this comparison. Specific studies to be considered will include the Cleveland study, and other studies identified prior to the analysis of actual trial data.

8.Informed Consent Process

The study protocol and informed consent will be reviewed and approved by Advarra Institutional Review Board prior to study start.

Study candidates will learn about the study via digital advertisements. If interested in learning more, they will be referred to a website "landing page" that will provide detailed information about the study. They may opt to complete a screening survey ascertaining study eligibility through patient reported outcomes. If successfully completed (no exclusion criteria are selected), candidate will be invited to review the study consent form tutorial which includes the opportunity to ask questions related to the study from the Principal Investigator or delegated authority of the investigator. Candidate will be proved with contact information to reach investigator or study manager as desired.

Candidate may sign the informed consent via electronic signature as provided by Hawthorne Effect. The study manager will verify candidate signature prior to enrollment as a study participant.

9. Subject Confidentiality

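### The Kaplan-Meier interval implied by the survival package default is too narrow on the first days of the curve at about 80 participants; naming a better one costs a sentence (minor).

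*Combined protocol and SAP*

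**What the plan says.** Under General statistical methods, section 7.3 gives the software rule: "Present intention is that the analysis will be performed in R, and the precise form of algorithms will be the default of R". For the survival methods it adds that "Kaplan-Meier, log-rank, and proportional hazards algorithms will be the defaults of the survival package". The same section leaves further detail to a SAP still to be prepared.

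Not everything is left to defaults. Section 7.3 itself chooses t-based intervals for means and exact intervals for discrete variables. For group comparisons of discrete variables it says: "Group comparisons will use Fisher's exact test, with the Monte Carlo version used where computationally necessary".

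For the primary analysis it promises tables, graphs and numbers at risk, and for the individual symptoms the Kaplan-Meier median. It names no Kaplan-Meier interval type, confidence level, replicate count, seed or software version. The planned side-by-side display with published studies includes, where possible, the share of symptoms resolved at each time.

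On size, section 5.1 sets a target of 200 enrolled "with a desired sample of 80 treated participants". Section 7.2 derives the 80 from an assumption that "approximately 40% of the enrolled participants in this trial will experience a cold during the 90-day period".

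**The concern.** This is a single-arm estimation study with no control group and no formal historical comparison. Any interval drawn round the recovery curve is therefore a main guide to how far the curve can be trusted. An analyst who follows section 7.3 literally would call `survfit` without an interval argument and get the log-scale interval, which is also plotted by default for a single curve.

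That interval behaves poorly when few participants have had the event. Before any censoring, the Kaplan-Meier estimate is a simple binomial proportion. The plan asks for an exact interval when such a proportion appears in a table of a discrete variable. The default would give the same proportion a weaker interval on the curve.

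At stake is the honesty of the 95% label on the first days of the descriptive curve and in the time-point display beside the historical studies. These results may also feed the design of a later two-arm trial.

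**Working it through.** **The plan's own figure.** 200 × 0.40 = 80, as section 7.2 states: "A sample size of 200 enrolled participants would then yield 80 participants with colds".

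**Inputs**
- n = 80 (sections 5.1 and 7.2).
- Confidence level 95% two-sided: not stated in the documents, assumed.
- Default interval `conf.type = log` with Greenwood variance, and default B = 2000 for Monte Carlo Fisher with simulation switched off: read from R 4.3.3 and survival 3.8.3. The documents state no version.
- S, the true proportion still ill on an early day: not in the documents. It is varied from 0.88 to 0.99, with 0.80 for contrast.

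**Formula.** With no censoring before the day and k of 80 resolved, the estimate is 1 − k/80 and the standard error of its logarithm is √(k / (80(80 − k))). The default limits are (1 − k/80) × exp(±1.96 × SE), capped at 1. Coverage is the sum of Binomial(80, 1 − S) probabilities over those k whose interval contains S.

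**Example, S = 0.96.**
- k = 0 gives [1, 1], and k = 1 gives [0.9635, 1]. Both lie wholly above 0.96.
- k = 2 gives [0.9414, 1], which covers.
- Misses above: 0.96^80 + 80 × 0.04 × 0.96^79 = 0.0382 + 0.1272 = 0.165.
- Misses below: about 0.005.
- Coverage: 1 − 0.165 − 0.005 = 0.830.

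**Example, S = 0.98.** Only k = 0 misses above, with probability 0.98^80 = 0.199. Misses below are about 0.001, so coverage is 0.800.

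**Results (%).** The last column uses log-log limits, replaced when k = 0 by the exact two-sided limit [0.025^(1/80), 1] = [0.955, 1]. Where S is at least 0.955, this adds S^80 to the log-log coverage. Entries come from unrounded values.

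| S | default log | log-log alone | chance of no resolutions | log-log + exact limit |
|---|---|---|---|---|
| 0.99 | 55.2 | 50.6 | 44.8 | 95.3 |
| 0.98 | 80.0 | 77.9 | 19.9 | 97.8 |
| 0.97 | 91.0 | 87.9 | 8.7 | 96.7 |
| 0.96 | 83.0 | 92.1 | 3.8 | 95.9 |
| 0.95 | 91.2 | 93.7 | 1.7 | 93.7 |
| 0.92 | 88.7 | 97.4 | 0.1 | 97.4 |
| 0.90 | 90.7 | 96.3 | <0.1 | 96.3 |
| 0.88 | 92.3 | 96.3 | <0.1 | 96.3 |
| 0.80 | 93.2 | 94.8 | <0.1 | 94.8 |

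Coverage is a sawtooth in S, so single rows should not be over-read. Averaged over S from 0.88 to 0.96, the default covers 91.2% and log-log 95.7%. The default's misses split into 8.2% wholly above the true S and 0.5% wholly below.

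**With censoring.** In simulated daily Weibull durations (18-day cut-off, 1% daily dropout), default coverage on day 1 was:
- median 7 days: 35% (shape 2.5), 71% (shape 2) and 79% (shape 1.5);
- median 4.5 days, shape 1.5: 92%.

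By days 2 to 3 it was 89 to 95%. The interval for the median covered at least 95% in every scenario.

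**Monte Carlo Fisher.**
- At p = 0.05 and B = 2000, the SE is √(0.05 × 0.95 / 2000) = 0.0049.
- Two runs differ with SD √2 × 0.0049 = 0.0069 and mean absolute difference (2/√π) × 0.0049 = 0.0055.
- At B = 100,000 the SE is 0.0007.
- Exact Fisher on example 3×3 and 3×4 tables, the latter of 80 participants, took about a millisecond.

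**The case against.** The strongest reply is that this is a standard default used in a descriptive study. The software rule is a present intention ahead of a later SAP. No Kaplan-Meier interval is a named output, nothing is decided on an early-day interval, and the median is well served. All of that stands, and it is why the point is minor.

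A second objection is that log-log alone is no remedy on the very first days. The table bears this out: from S = 0.97 upwards it covers slightly less than the default, because both collapse to [1, 1] with no resolutions. This changes the remedy, which needs the exact limit, but does not defeat it.

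Third, the early S is assumed. A cold that resolves fast shows little of the problem even on day 1, as the 4.5-day scenario shows. That also stands.

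A reader might infer three stronger things that the documents do not support:
- That the plan locks every algorithm to a default. It names several methods outright and describes the rest as an intention.
- That the primary result is unreliable. The shortfall is early in the curve and does not extend to the median.
- That Fisher p-values near 0.05 will swing by about 0.01 from run to run. That figure is the 95% half-width of a single run (1.96 × 0.0049 = 0.0096), and simulation is foreseen only as a fallback: "with the Monte Carlo version used where computationally necessary".

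**Conclusion.** The point holds as a minor one. If the stated intention is followed, the nominal 95% interval at n = 80 covers about 91% on average while 88 to 96% are still ill. It falls well below that while 98% or more are still ill, mainly because an interval with no width is reported when nobody has resolved. The errors are one-sided: when the interval misses, it nearly always overstates the proportion still ill. It would therefore tend to understate early recovery, and a reader should not infer a tilt in the product's favour.

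The conclusion rests on the software defaults as read, a 95% level, about 80 treated participants, and assumed early-day proportions. It affects the early part of the descriptive curve and the time-point display beside historical studies. The Fisher part is a reproducibility note only.

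**What to change.** In section 7.3, after the sentence on survival package defaults, add:

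> except that pointwise Kaplan-Meier 95% confidence intervals use the log-log transformation, with an exact binomial limit (two-sided, based on the number at risk) on days when no participant has yet resolved; if a Monte Carlo Fisher test is needed, it uses at least 100,000 replicates with a recorded seed.

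The detailed SAP should repeat this and record the R and package versions.

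At n = 80 this gives about 94 to 98% coverage at the early-day proportions tabulated. Narrow dips remain between them. For example, just above S = 0.9937, the upper log-log limit for k = 2, coverage is 0.9937^80 + 80 × 0.0063 × 0.9937^79 = 0.603 + 0.306 = about 91%. The change does not help the far tail, where every interval tried loses coverage once S falls below about 0.03.

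The cost is one sentence, one function argument for the interval, a short rule for days without resolutions, and a replicate count and seed if simulation is used. No extra data, participants or visits are needed.

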13.1. Appendix

13.1.1. Appendix A Drug Interactions

Drug Interactions for Test Product

ECHINACEA

There are no Serious Drug Interactions known for Echinacea. There are some theoretical Moderate Interactions, where Echinacea may interact in the metabolism of certain drugs (which utilize the same enzymes it inhibits). See Below for List. Echinacea theoretically may also interfere with immunosuppressant therapy drugs due to its immune-stimulating activity.

CAFFEINE

Interaction Rating = **Moderate** Be cautious with this combination. Severity = Mild • Occurrence = Probable • Level of Evidence = **B**

Echinacea seems to increase plasma concentrations of caffeine by 30% (12155). This is likely due to inhibition of cytochrome P450 1A2 (CYP1A2) by echinacea.

CYTOCHROME P450 1A2 (CYP1A2) SUBSTRATES

Interaction Rating = **Moderate** Be cautious with this combination. Severity = Moderate • Occurrence = Possible • Level of Evidence = **B**

Echinacea appears to inhibit CYP1A2 enzymes in humans (12155). Theoretically, echinacea might increase levels of drugs metabolized by CYP1A2. Some drugs metabolized by CYP1A2 include acetaminophen (Tylenol), amitriptyline (Elavil), clopidogrel (Plavix), clozapine (Clozaril), diazepam (Valium), estradiol, olanzapine (Zyprexa), ondansetron (Zofran), propranolol (Inderal), ropinirole (Requip), tacrine (Cognex), theophylline, verapamil (Calan, Covera-HS, Isoptin, Verelan), warfarin (Coumadin), and others.

CYTOCHROME P450 3A4 (CYP3A4) SUBSTRATES

Interaction Rating = **Moderate** Be cautious with this combination. Severity = Moderate • Occurrence = Possible • Level of Evidence = **B**

Several clinical trials have shown that taking echinacea for up to one month does not significantly affect the metabolism of various cytochrome P450 3A4 (CYP3A4) substrates, including midazolam, docetaxel, etrovine, lopinavir-ritonavir, and darunavir-ritonavir (13712,48618,88164,88165). However, other clinical research shows that echinacea may increase the clearance of midazolam, suggesting that echinacea might induce CYP3A4 (48618). The discrepancy is thought to be due to differing effects of echinacea on intestinal versus

hepatic CYP3A4 enzymes. Echinacea appears to induce hepatic CYP3A4 and inhibit intestinal CYP3A4 (12155). In some cases, these effects might cancel out each other, resulting in little or no change in drug levels. In other cases, drug levels may be increased or decreased depending on the extraction of drugs at hepatic and intestinal sites. The effect of echinacea on CYP3A4 activity may differ depending on the CYP3A4 substrate (6450,11026,88162,88167). For now, closely monitor patients taking echinacea along with drugs metabolized by CYP3A4. Theoretically, echinacea may alter the effects and side effects of these drugs. Some drugs metabolized by CYP3A4 include lovastatin (Mevacor), clarithromycin (Biaxin), cyclosporine (Neoral, Sandimmune), diltiazem (Cardizem), estrogens, indinavir (Crixivan), triazolam (Halcion), and numerous others.

DARUNAVIR (Prezista)

Interaction Rating = **Minor** Be watchful with this combination.

Severity = Insignificant • Occurrence = Unlikely • Level of Evidence = **B**

Darunavir is metabolized by cytochrome P450 3A4 (CYP3A4) and is administered with the CYP3A4 inhibitor ritonavir to increase its plasma concentrations. Echinacea has variable effects on CYP3A4, but administration of an E. purpurea root extract (Arkocapsulas Echinacea, Arkopharma, Madrid, Spain) 500 mg four times daily for 14 days did not affect darunavir / ritonavir pharmacokinetics in 15 HIV-infected patients (88163,93578).

DOCETAXEL (Docefrez, Taxotere)

Interaction Rating = Minor Be watchful with this combination.

Severity = Insignificant • Occurrence = Unlikely • Level of Evidence = **B**

Docetaxel is metabolized by cytochrome P450 3A4 (CYP3A4). Echinacea has variable effects on CYP3A4, but taking E. purpurea whole plant extract (Echinaforce, A. Vogel Biopharma AG, Elburg, The Netherlands) 20 drops three times daily for 2 weeks did not alter the pharmacokinetics of docetaxel given as an intravenous infusion of 135 mg over one hour (88164).

ETOPOSIDE (VePesid)

Interaction Rating = Moderate Be cautious with this combination.

Severity = Moderate • Occurrence = Possible • Level of Evidence = **D**

In one report, concomitant use of etoposide and echinacea was associated with more severe thrombocytopenia than the use of etoposide alone, suggesting inhibition of etoposide metabolism (20082). Etoposide is a cytochrome P450 3A4 (CYP3A4) substrate. Echinacea has variable effects on CYP3A4, but some studies have reported inhibition of the enzyme (6450,11026,12155,88162,88167).

ETRAVIRINE (Intelence)

Interaction Rating = **Minor** Be watchful with this combination.

Severity = Insignificant • Occurrence = Unlikely • Level of Evidence = **B**

Etravirine is metabolized by cytochrome P450 3A4 (CYP3A4). Echinacea has variable effects on CYP3A4, but taking E. purpurea root extract (Arkocapsulas Echinacea, Arkopharma, Madrid, Spain) 500 mg three times daily for 14 days did not alter the pharmacokinetics of etravirine in HIV-infected patients (88165,93578).

IMMUNOSUPPRESSANTS

Interaction Rating = **Moderate** Be cautious with this combination. Severity = High • Occurrence = Possible • Level of Evidence = **B**

Theoretically, echinacea may interfere with immunosuppressant therapy because of its immunostimulating activity (3279,6388,6389,12639). Immunosuppressant drugs include azathioprine (Imuran), basiliximab (Simulect), cyclosporine (Neoral, Sandimmune), daclizumab (Zenapax), muromonab-CD3 (OKT3, Orthoclone OKT3), mycophenolate (CellCept), tacrolimus (FK506, Prograf), sirolimus (Rapamune), prednisone (Deltasone, Orasone), and other corticosteroids (glucocorticoids).

LOPINAVIR/RITONAVIR (Kaletra)

Interaction Rating = **Minor** Be watchful with this combination.

Severity = Insignificant • Occurrence = Unlikely • Level of Evidence = **B**

Lopinavir is metabolized by cytochrome P450 3A4 (CYP3A4) and is administered with the CYP3A4 inhibitor ritonavir to increase its plasma concentrations. Echinacea has variable effects on CYP3A4, but taking E. purpurea (Echinamide, Natural Factors Nutritional Products, Inc., Everett, WA) 500 mg three times daily for 14 days did not alter the pharmacokinetics of lopinavir / ritonavir in healthy volunteers (48618,93578).

MIDAZOLAM (Versed)

Interaction Rating = Minor Be watchful with this combination.

Severity = Insignificant • Occurrence = Possible • Level of Evidence = **B**

Echinacea appears to inhibit intestinal cytochrome P450 3A4 (CYP3A4), leading to an increase in oral midazolam availability. Echinacea also appears to induce hepatic CYP3A4, increasing hepatic clearance of midazolam by 34%. Overall, plasma levels of midazolam after oral administration do not seem to be affected by echinacea. However, theoretically, echinacea might decrease the effectiveness of intravenous midazolam by inducing hepatic CYP3A4 and lowering plasma levels by about 20% (12155).

WARFARIN (Coumadin)

Interaction Rating = **Minor** Be watchful with this combination.

Severity = Insignificant • Occurrence = Possible • Level of Evidence = **B**

Preliminary clinical research in healthy male volunteers suggests that taking echinacea increases the clearance of the active S-isomer of warfarin after a single dose of warfarin, but there was not

a clinically significant effect on the international normalized ratio (INR) (20083). Patients taking warfarin should be advised to use echinacea cautiously.

Interactions with Herbs & Supplements

None known.

IVY EXTRACT

There are no Serious Drug Interactions known for Ivy Extract.

None known.

Interactions with Herbs & Supplements

None known

ACEROLA, VITAMIN C

There are no Serious Drug Interactions known for Acerola. There are a couple theoretical Moderate Interactions having to do with its Vitamin C content, however.

ESTROGENS

Interaction Rating = **Minor** Be watchful with this combination.

Severity = Mild • Occurrence = Possible • Level of Evidence = **D**

Concomitant use of estrogens with acerola might increase absorption and therapeutic effects due to vitamin C content $(\underline{129,130})$.

FLUPHENAZINE (Prolixin)

Interaction Rating = **Moderate** Be cautious with this combination.

Severity = Moderate • Occurrence = Possible • Level of Evidence = **D**

Concomitant use with acerola decreases blood levels due to vitamin C content (15).

WARFARIN (Coumadin)

Interaction Rating = **Moderate** Be cautious with this combination.

Severity = High • Occurrence = Possible • Level of Evidence = **D**

Concomitant use with acerola can reduce anticoagulant activity of warfarin due to its vitamin C content (506).

Interactions with Herbs & Supplements

VITAMIN C: Due to vitamin C content in acerola, concomitant use of acerola with vitamin C supplements might increase the risk of adverse effects associated with vitamin C.

GINGER

There are no Serious Drug Interactions known for Ginger. There are some theoretical Moderate Interactions having to do with the potential of ginger in decreasing platelet aggregation. See Below for List.

ANTICOAGULANT/ANTIPLATELET DRUGS

Interaction Rating = **Moderate** Be cautious with this combination. Severity = High • Occurrence = Possible • Level of Evidence = **B**

Based on laboratory research, ginger is thought to inhibit thromboxane synthetase and decrease platelet aggregation (7622,12634,20321,20322,20323,96257). However, this has not been demonstrated unequivocally in humans, with mixed results from clinical trials (96257). Theoretically, excessive amounts of ginger might increase the risk of bleeding when used with anticoagulant/antiplatelet drugs. Some anticoagulant or antiplatelet drugs include aspirin, clopidogrel (Plavix), dalteparin (Fragmin), enoxaparin (Lovenox), heparin, ticlopidine (Ticlid), warfarin (Coumadin), and others.

ANTIDIABETES DRUGS

Interaction Rating = **Minor** Be watchful with this combination. Severity = Moderate • Occurrence = Unlikely • Level of Evidence = **D**

Evidence from animal and human research suggests that ginger might increase insulin levels and/or decrease blood glucose levels (12636,20402,20403,20404,20405,89895,89896). Theoretically, ginger might have an additive effect with antidiabetes drugs and cause hypoglycemia. Some antidiabetes drugs include glimepiride (Amaryl), glyburide (DiaBeta, Glynase PresTab, Micronase), insulin, metformin (Glucophage), pioglitazone (Actos), rosiglitazone (Avandia), and others.

CALCIUM CHANNEL BLOCKERS

Interaction Rating = **Minor** Be watchful with this combination.

Severity = Moderate • Occurrence = Unlikely • Level of Evidence = **D**

Preliminary research suggests ginger might have hypotensive and calcium channel-blocking effects (12633). Theoretically, ginger might have an additive effect with calcium channel blockers. Calcium channel blockers include nifedipine (Adalat, Procardia), verapamil (Calan, Isoptin, Verelan), diltiazem (Cardizem), isradipine (DynaCirc), felodipine (Plendil), amlodipine (Norvasc), and others.

CYCLOSPORINE (Neoral, Sandimmune)

Interaction Rating = Minor Be watchful with this combination.

Severity = Mild • Occurrence = Possible • Level of Evidence = **D**

In an animal model, ginger juice taken 2 hours prior to cyclosporine administration reduced the maximum concentration and area under the curve of cyclosporine by 51.4% and 40.3%, respectively. This effect was not observed when ginger juice and cyclosporine were administered at the same time (20401).

METRONIDAZOLE (Flagyl)

Interaction Rating = **Minor** Be watchful with this combination.

Severity = Mild • Occurrence = Possible • Level of Evidence = **D**

In an animal model, ginger increased the absorption and plasma half-life of metronidazole. In addition, the elimination rate and clearance of metronidazole was significantly reduced (20350).

NIFEDIPINE

Interaction Rating = **Moderate** Be cautious with this combination.

Severity = Moderate • Occurrence = Possible • Level of Evidence = **B**

Clinical research shows that combined treatment with ginger 1 gram plus nifedipine 10 mg significantly inhibits platelet aggregation compared to nifedipine alone or ginger alone (20324).

PHENPROCOUMON

Interaction Rating = **Moderate** Be cautious with this combination.

Severity = High • Occurrence = Possible • Level of Evidence = **D**

Phenprocoumon, a warfarin-related anticoagulant used in Europe, might increase the international normalized ratio (INR) when taken with ginger. There is one case report of a 76 year old woman with a stable INR on phenprocoumon that increased to greater than 10 when she began consuming dried ginger and ginger tea (12880).

WARFARIN (Coumadin)

Interaction Rating = **Moderate** Be cautious with this combination. Severity = High • Occurrence = Possible • Level of Evidence = **B**

Preliminary evidence suggests that ginger might inhibit thromboxane synthetase and decrease platelet aggregation (7622,12634,20321,20322,20323). In one case report, ginger increased the INR when taken with phenprocoumon, which has similar pharmacological effects as warfarin (12880). In another case report, ginger increased the INR when taken with a combination of warfarin, hydrochlorothiazide, and acetaminophen (20349). A longitudinal analysis suggests that taking ginger increases the risk of bleeding in patients taking warfarin for at least 4 months (20348). However, research in healthy people suggests that ginger has no effect on INR, or the pharmacokinetics or pharmacodynamics of warfarin (12881,15176). Until more is known, monitor INRs closely in patients taking significant amounts of ginger.

Interactions with Herbs & Supplements

ANTICOAGULANT/ANTIPLATELET HERBS AND SUPPLEMENTS: Based on laboratory research, ginger is thought to inhibit thromboxane synthetase and decrease platelet aggregation (7622,12634,20321,20322,20323). However, this has not been demonstrated unequivocally in humans with mixed results from clinical trials (96257). Concomitant use of ginger with other herbs that might affect platelet aggregation could theoretically increase the risk of bleeding in some people. These herbs include angelica, clove, danshen, garlic, ginkgo, Panax ginseng, red clover, turmeric, and others.

HERBS AND SUPPLEMENTS WITH HYPOGLYCEMIC POTENTIAL: Ginger might increase insulin levels and/or decrease blood glucose levels (12636,20402,20403,20404,20405,89895,89896). Theoretically, ginger might have additive effects with herbs that decrease blood glucose levels. Herbs with hypoglycemic potential include devil's claw, fenugreek, guar gum, Panax ginseng, and Siberian ginseng.

TURMERIC

There are no Serious Drug Interactions known for Turmeric. There are some theoretical Moderate Interactions, however, see below for list.

ANTICOAGULANT/ANTIPLATELET DRUGS

Interaction Rating = **Moderate** Be cautious with this combination. Severity = High • Occurrence = Possible • Level of Evidence = **D**

In vitro, turmeric has been shown to have antiplatelet effects (11143,81204,81271). However, results from human research are inconsistent. Turmeric has reportedly increased in the international normalized ratio (INR) in a patient using the vitamin K antagonist, fluindione (89718). However, use of a whole food supplement containing broccoli powder, turmeric

powder, pomegranate whole fruit powder, and green tea extract for 6 months does not influence INR in men taking warfarin (89730). Also, combining curcumin 500 mg with aspirin 100 mg does not appear to increase antiplatelet effects or bleeding risk (96137). Until more is known, use turmeric cautiously in combination with anticoagulant and antiplatelet drugs. Theoretically, concomitant use might increase the risk of bleeding due to decreased platelet aggregation. Some of these drugs include aspirin, clopidogrel (Plavix), dalteparin (Fragmin), enoxaparin (Lovenox), heparin, ticlopidine (Ticlid), warfarin (Coumadin), and others.

ANTIDIABETES DRUGS

Interaction Rating = **Moderate** Be cautious with this combination. Severity = Moderate • Occurrence = Possible • Level of Evidence = **B**

Animal research and case reports suggests that the turmeric constituent, curcumin, can reduce levels of blood glucose and glycosylated hemoglobin (HbA1C) in patients with diabetes (79114,79573,79591,79692,79984,80155,80313,80315,80476,80553)(81048,81219). Furthermore, pharmacokinetic research shows that taking curcumin 475 mg daily for 10 days prior to taking glyburide 5 mg increases blood levels of glyburide by 12% at 2 hours after the dose in patients with type 2 diabetes. While maximal blood concentrations of glyburide were not affected by curcumin, the combination of curcumin and glyburide modestly decreased postprandial glucose levels for up to 24 hours compared to glyburide alone (96133). Theoretically, taking a combination of turmeric and antidiabetes drugs might have an additive effect and increase the risk of hypoglycemia. Some medications used for diabetes include glimepiride (Amaryl), glyburide (DiaBeta, Glynase PresTab, Micronase), insulin, pioglitazone (Actos), rosiglitazone (Avandia), chlorpropamide (Diabinese), glipizide (Glucotrol), tolbutamide (Orinase), and others.

CAMPTOTHECIN

Interaction Rating = **Moderate** Be cautious with this combination. Severity = High • Occurrence = Possible • Level of Evidence = **D**

One in vitro study suggests that curcumin inhibits camptothecin-induced apoptosis of breast cancer cells by up to 71% (96126). However, other in vitro research shows that curcumin can augment the cytotoxic effects of camptothecin. Reasons for the discrepancies may relate to the dose of curcumin and the timing of curcumin exposure (96125). It is not known if turmeric or its constituent curcumin inhibits or augments the cytotoxicity camptothecin in humans. Until more is known, use turmeric cautiously in combination with camptothecin. Theoretically, concomitant use of turmeric with camptothecin would reduce the efficacy of camptothecin.

CYCLOPHOSPHAMIDE

Interaction Rating = **Moderate** Be cautious with this combination. Severity = High • Occurrence = Possible • Level of Evidence = **D**

In an animal model of breast cancer, curcumin 25 grams/kg appears to inhibit cyclophosphamide-induced tumor regression (96126). However, other laboratory research shows that curcumin can augment the cytotoxic effects of cyclophosphamide. Reasons for the

discrepancies may relate to the dose and timing of curcumin exposure (96125). It is not known if turmeric or its constituent curcumin inhibits or augments the cytotoxicity cyclophosphamide in humans. Until more is known, use turmeric cautiously in combination with cyclophosphamide. Theoretically, concomitant use of turmeric with cyclophosphamide might reduce the efficacy of cyclophosphamide.

CYTOCHROME P450 1A1 (CYP1A1) SUBSTRATES

Interaction Rating = **Minor** Be watchful with this combination. Severity = Mild • Occurrence = Possible • Level of Evidence = **D**

Most evidence from in vitro and animal research suggests that the turmeric constituent, curcumin, suppresses cytochrome P450 1A1 (CYP1A1) enzyme, primarily in the liver (15823,21495,80876,81411). However, some evidence from in vitro research suggests that curcumin may induce CYP1A1 in the intestines (21500). Theoretically, curcumin might increase or decrease levels of drugs metabolized by this enzyme. However, this interaction has not been reported in humans. Some medications metabolized by CYP1A1 include chlorzoxazone (Lorzone), theophylline, and bufuralol.

CYTOCHROME P450 1A2 (CYP1A2) SUBSTRATES

Interaction Rating = **Minor** Be watchful with this combination. Severity = Mild • Occurrence = Possible • Level of Evidence = **D**

In vitro and animal research shows that the turmeric constituent, curcumin, inhibits cytochrome P450 1A2 (CYP1A2) enzyme (15823,21497,81304). Theoretically, curcumin might increase levels of drugs metabolized by this enzyme. However, other in vitro research suggests that curcumin does not significantly affect CYP1A2 (22000). Also, this interaction has not been reported in humans. Some substrates of CYP1A2 include clozapine (Clozaril), cyclobenzaprine (Flexeril), fluvoxamine (Luvox), haloperidol (Haldol), imipramine (Tofranil), mexiletine (Mexitil), olanzapine (Zyprexa), pentazocine (Talwin), propranolol (Inderal), tacrine (Cognex), zileuton (Zyflo), zolmitriptan (Zomig), and others.

CYTOCHROME P450 3A4 (CYP3A4) SUBSTRATES

Interaction Rating = **Moderate** Be cautious with this combination. Severity = Moderate • Occurrence = Possible • Level of Evidence = **D**

